3.3.3 Safety Outcome Measures

Safety will be assessed through regular neurological and physical examinations (including vital signs), prospective suicidality assessment (copyright Pfizer Inc. and Janssen Alzheimer Immunotherapy; used with permission), laboratory tests, ECGs, and MRI assessments. In addition, the following data will be collected and analyzed:

- Frequency and severity of treatment-emergent adverse events and serious adverse events
- Withdrawals due to adverse events
- Incidence of injection reactions and IRRs
- Incidence of anti-crenezumab antibodies
- Incidence of treatment-emergent adverse events of special interest, including:
 - ARIA-E (cerebral VE, sulcal effusion)
 - ARIA-H (superficial CNS siderosis, cerebral microhemorrhages)
 - Cerebral macrohemorrhages
 - Pneumonia

3.3.4 Pharmacokinetic/Pharmacodynamic Outcome Measures

The PK outcome measures are CSF and serum crenezumab concentrations at protocol-specified timepoints. In serum, crenezumab $C_{trough, ss}$ will be assessed. Additional PK analyses may be conducted, as appropriate.

The PD outcome measures are as follows: plasma A β 1–40 and A β 1–42 concentrations.

3.3.5 Exploratory Outcome Measures

Exploratory outcome measures are listed below. In addition, any endpoints (among those listed in Section 3.3.2) that are not prespecified in the SAP as secondary outcome measures may be analyzed as exploratory outcome measures.

3.3.5.1 Clinical

- Changes from baseline over time in the following cognitive measures:
 - Trail Making Test (Armitage 1946)
 - MMSE (Folstein et al. 1975)
 - RBANS Index Scores (Randolph 1998)
 - Scores of each of the components of the API ADAD Composite Cognitive Test Battery
 - Preclinical Alzheimer’s Cognitive Composite (PACC) (Donohue et al. 2014), which for this trial will include the FCSRT free and cued recall, MMSE, RBANS story recall, and RBANS coding score
 - Clinical endpoints not examined in secondary outcome measures
- Changes in the Neuropsychiatric Inventory (NPI) (Cummings et al. 1994; Cummings 1997) total score, items, and factors
- Changes in the Geriatric Depression Scale (GDS) (Sheikh and Yesavage 1986) total score
- Changes in Functional Assessment Staging of Alzheimer’s Disease (FAST) (Sclan and Reisberg 1992) total score
- Changes in Subjective Memory Checklist (SMC, Acosta-Baena et al. 2011)

3.3.5.2 Fluid Biomarkers

- CSF levels of A β species
- Changes in other blood and CSF measures

3.3.5.3 Imaging Biomarkers

- Analysis of ROIs not selected in secondary outcome measures
- Other imaging outcome measures and analytic methods, alone, or in conjunction with other imaging modalities not explored in secondary outcome measures
- Change in tau burden over time, as measured by [^{18}F]-Genentech Tau Probe 1 (GTP1) PET in an optional substudy (GN28352-1/BN40199)

3.3.5.4 Other Outcome Measures

- Changes in primary, secondary, and exploratory outcomes in mutation non-carriers treated with placebo
- Comparisons of clinical and biomarker outcomes between carriers treated with placebo and non-carriers
- Changes in primary, secondary, and exploratory outcomes in carriers and non-carriers as functions of *APOE* genotype and other genetic variations
- Short-term changes in imaging measures as functions of initiation (e.g., baseline to 12 weeks)
- Analyses of outcome measures in relation to one another and in relation to baseline characteristics

3.4 OUTCOME MEASURES IN STUDY PERIOD B

The same safety, efficacy, and PK and PD measures will be collected in Study Period B with the exception of FDG-PET (see [Appendix 5](#) and [Appendix 6](#) for frequency of assessments). The safety outcome measures are as described for Study Period A. Efficacy and PK/PD outcome measures will be assessed as change over time for continuous outcome measures or time to event for time to progression to non-zero in the CDR Scale global score and for progression from preclinical AD to MCI due to AD or from preclinical AD to Dementia due to AD.

3.5 SAFETY PLAN

See Section [5](#) for complete details of the safety evaluation for this study.

Crenezumab has not been approved for use by global health authorities and is currently in clinical development. Thus, the entire safety profile is not known at this time. The crenezumab safety information is based on results from nonclinical and clinical studies, as well as published data on similar molecules. The safety monitoring for this study is designed to ensure participant safety and will include specific eligibility criteria and monitoring assessments. Any adverse events/serious adverse events or any other abnormalities (e.g., laboratory assessments, radiographs, physical examination findings) should be managed by the site investigators, as medically appropriate (unless otherwise specified in the protocol).

The safety of participants in this trial will be ensured through the use of stringent inclusion and exclusion criteria and through close monitoring of participants.

Investigators will assess the occurrence of adverse events and serious adverse events at all participant evaluation timepoints during the study. All adverse events and serious adverse events, whether volunteered by the participant, discovered by study personnel during questioning, or detected through physical examination, laboratory tests, or other means, will be recorded in the participant's medical record and on the appropriate adverse event or serious adverse event electronic Case Report Form (eCRF).

Each recorded adverse event or serious adverse event will include a description of its duration (i.e., start and end dates), severity, seriousness according to regulatory criteria, if applicable, and suspected relationship to the investigational product, as well as any actions taken.

Participants will be followed carefully for adverse events during the study, including a 4-week postdose visit and a final safety follow-up visit 16 weeks after the last dose of study drug (for the list of study assessments, see the study flowcharts in [Appendix 1](#) to [Appendix 4](#)). Adverse events will be graded according to severity using the National Cancer Institute Common Terminology Criteria for Adverse Events (NCI CTCAE), Version 4.0.

An independent Data Monitoring Committee (iDMC) formerly known as the Data and Safety Monitoring Board (DSMB) will be used for this study *during Study Period A*. *During Study Period B, an internal data monitoring committee comprised of Sponsor employees not affiliated with the trial will monitor safety.*

Please refer to the latest Crenezumab Investigator's Brochure for additional safety information.

3.5.1 Immunogenicity

Immunogenicity, as determined by the presence of a positive response in the ADA enzyme-linked immunosorbent assay (ELISA), will be assessed at specified timepoints during the course of the study. Additional characterizations will be performed if necessary.

3.5.2 Amyloid-Related Imaging Abnormalities

Amyloid-related imaging abnormalities are a spectrum of image abnormalities detected on MRI. Two types of ARIA have been described: Amyloid-related imaging abnormalities–effusion refers to the MRI alterations thought to represent VE and related extravasated fluid phenomena, and ARIA-H refers to the MRI alterations attributable to microhemorrhages and leptomeningeal hemosiderosis.

The occurrence of imaging abnormalities believed to represent cerebral VE has been reported in association with the investigational use of compounds that are intended to treat AD by reducing A β in the brain. These imaging abnormalities (Salloway et al. 2009; Sperling et al. 2011a) have, in the majority of instances, been asymptomatic, and their presence has been detected by brain MRI. Symptoms, when present in association with such imaging abnormalities, have been reported to include headache, worsening cognitive function, alteration of consciousness, seizures, unsteadiness, and vomiting.

The clinical significance of ARIA-H is not yet fully understood.

When anti-A β antibodies bind to amyloid deposited around blood vessels, an Fc γ R-mediated immune response may be elicited, compromising vascular integrity and resulting in ARIA-E or ARIA-H. Crenezumab, a human IgG4, has reduced Fc γ R binding compared with IgG1/2 and, thus, has reduced effector function that theoretically may lower the risk of ARIA-E. This has been supported by emerging safety data observed in both clinical and nonclinical studies conducted to date. A lack of binding to vascular amyloid, noted following in vivo dosing in PS2APP Tg mice (Study 15-2817B), may additionally reduce the risk of ARIA.

To minimize the potential safety risks associated with ARIA-E and ARIA-H in this study, participants will be screened for ARIA-E and ARIA-H before enrollment and will be monitored for ARIA-E and ARIA-H by MRI during treatment (see Section 3.5.2.1). Given the uncertainty of risk and concerns about cerebral amyloid angiopathy (CAA) severity, participants with superficial siderosis of the CNS, more than 4 cerebral microhemorrhages, or evidence of a prior cerebral macrohemorrhage at screening will be excluded from this study.

An overview of the monitoring and management guidelines for ARIA-E and ARIA-H is provided in the following sections.

The cerebral microhemorrhage thresholds for study entry and treatment discontinuation allow for imaging measurement variability to be taken into account and reflect the uncertainty regarding the clinical relevance of small numbers of cerebral microhemorrhages. This approach is intended to minimize potential safety risks associated with cerebral microhemorrhages but would not preclude participants from receiving potentially beneficial treatment (see Section 3.5.2.2).

3.5.2.1 Monitoring for Amyloid-Related Imaging Abnormalities

In this Phase II study, a safety monitoring plan has been designed to mitigate and monitor the potential risk of ARIA-E and ARIA-H associated with anti-A β immunotherapy. This plan consists of the following key elements:

- Participants with evidence of one or more of the following abnormalities assessed by MRI during screening will be excluded from the trial:
 - Significant cerebral vascular pathology
 - Superficial siderosis of the CNS
 - More than 4 cerebral microhemorrhages
 - Evidence of a prior cerebral macrohemorrhage
- Participants enrolled in the study will regularly undergo neurological examinations to evaluate for any neurologic signs or symptoms that are suggestive of the presence of the following:

Cerebral VE (e.g., confusion, dizziness, vomiting, and lethargy), superficial siderosis of the CNS (e.g., sensorineural deafness, cerebellar ataxia, and

- pyramidal signs), or cerebral microhemorrhages (e.g., transient or permanent focal motor or sensory impairment, ataxia, aphasia, and dysarthria)
- Brain MRI examinations for *Study Period A* (including fluid-attenuated inversion recovery [FLAIR] and T2 with additional in-homogeneous dephasing (T2*)-weighted gradient-recalled echo [GRE] sequences) will be performed for safety monitoring approximately every 3 months for the first year and approximately every 6 months thereafter to detect potential safety risks noted below. If switching to 60 mg/kg IV Q4W, MRI scans will be performed at 3 months and 6 months after initiating the higher dose and then every 24–28 weeks thereafter to detect the following: ARIA-E, ARIA-H, and cerebral macrohemorrhages (see study flowchart in [Appendix 1](#), [Appendix 2](#), [Appendix 3](#), and [Appendix 4](#) for MRI schedule).

Brain MRI examinations in Study Period B will be done at Week 105 and as directed by symptoms.

All safety MRI scans will be read for the evaluation of ARIA-E, ARIA-H, and cerebral macrohemorrhages by independent radiologists at a central reading facility

- Regardless of severity, all events of cerebral VE, sulcal effusion, superficial siderosis of the CNS, and cerebral micro- or macro-hemorrhage that occur at any time after receiving study drug are considered to be adverse events of special interest and will be reported in an expedited manner (see Section 5.4)

3.5.2.2 Management of Amyloid-Related Imaging Abnormalities

Amyloid-Related Imaging Abnormalities—Edema/Effusion (ARIA-E)

The following rules for the management of MRI-related findings apply for ARIA-E:

- Asymptomatic ARIA-E with Size < 4 BGTS (Barkhof et al. 2013)
 - Continue study drug at the same dose (i.e., 60 mg/kg crenezumab)
 - Repeat MRI 4 weeks later
 - If ARIA-E is stable or decreased, continue study drug and monthly MRI monitoring until event resolves. Once ARIA-E completely resolves, conduct MRI monitoring as per study flowchart.
 - If ARIA-E increases (BGTS ≥ 4) or symptoms develop, see the rules below.
- Symptomatic ARIA-E (of any size) or asymptomatic ARIA-E with size ≥ 4 BGTS:
 - Temporarily interrupt study drug and implement monthly MRI monitoring
 - Once symptoms and ARIA-E resolve, reintroduce study drug and perform an MRI after 4 weeks of dosing. If no new MRI abnormality is detected, resume MRI monitoring as per the study flowchart.
- For any new onset of ARIA-E:
 - Treat the same as the first event, on the basis of symptoms and BGTS

- If a participant is diagnosed with 3 recurrent, symptomatic ARIA-E events or exacerbations of previous events, permanently discontinue the study drug
- Implement monthly MRI monitoring until resolution of both symptoms and ARIA-E
- As per the protocol, maintain the participant in the study until study end and perform assessments as per the study flowcharts

Amyloid-Related Imaging Abnormalities–Hemosiderin Deposition (ARIA-H)

The following dose adjustments and discontinuation rules for MRI-related findings will apply to ARIA-H:

- Dose reduction: Participants who develop >8 ARIA-H cumulatively will receive a lower dose of the study drug. Cumulative is the sum of ARIA-H at baseline and newly detected ARIA-H during the study.
- Study drug discontinuation: Participants who develop >10 ARIA-H cumulatively will be permanently discontinued from the study drug. Cumulative is the sum of ARIA-H at baseline and newly detected ARIA-H during the study.

The Sponsor believes that the above rules, coupled with frequent MRI monitoring and collection of CNS symptoms, will ensure safety while trying to maximize benefit for the participants.

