Cerebral VE (e.g., confusion, dizziness, vomiting, and lethargy), superficial siderosis of the CNS (e.g., sensorineural deafness, cerebellar ataxia, and pyramidal signs), or cerebral microhemorrhages (e.g., transient or permanent focal motor or sensory impairment, ataxia, aphasia, and dysarthria)
- Brain MRI examinations for *Study Period A* (including fluid-attenuated inversion recovery [FLAIR] and T2 with additional in-homogeneous dephasing (T2*)-weighted gradient-recalled echo [GRE] sequences) will be performed for safety monitoring approximately every 3 months for the first year and approximately every 6 months thereafter to detect potential safety risks noted below. If switching to 60 mg/kg IV Q4W, MRI scans will be performed at 3 months and 6 months after initiating the higher dose and then every 24–28 weeks thereafter to detect the following: ARIA-E, ARIA-H, and cerebral macrohemorrhages.

Brain MRI examinations in Study Period B will be done at Week 105 and as directed by symptoms. All safety MRI scans will be read for the evaluation of ARIA-E, ARIA-H, and cerebral macrohemorrhages by independent radiologists at a central reading facility
- Regardless of severity, all events of cerebral VE, sulcal effusion, superficial siderosis of the CNS, and cerebral micro- or macro-hemorrhage that occur at any time after receiving study drug are considered to be adverse events of special interest and will be reported in an expedited manner

Management of Amyloid-Related Imaging Abnormalities

Amyloid-Related Imaging Abnormalities—Edema/Effusion (ARIA-E)

The following rules for the management of MRI-related findings apply for ARIA-E:

- Asymptomatic ARIA-E with Size < 4 Barkhof Grand Total Score (BGTS)
 - Continue study drug at the same dose (i.e., 60 mg/kg crenazumab)
 - Repeat MRI 4 weeks later
 - If ARIA-E is stable or decreased, continue study drug and monthly MRI monitoring until event resolves. Once ARIA-E completely resolves, conduct MRI monitoring as per study flowchart.
 - If ARIA-E increases (BGTS ≥ 4) or symptoms develop, see the rules below.
- Symptomatic ARIA-E (of any size) or asymptomatic ARIA-E with size ≥ 4 BGTS:
 - Temporarily interrupt study drug and implement monthly MRI monitoring
 - Once symptoms and ARIA-E resolve, reintroduce study drug and perform an MRI after 4 weeks of dosing. If no new MRI abnormality is detected, resume MRI monitoring as per the study flowchart.
- For any new onset of ARIA-E:

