3. STUDY DESIGN

3.1 DESCRIPTION OF THE STUDY

Study Period A: This is a prospective, randomized, double-blind, placebo-controlled, parallel-group study of crenezumab versus placebo in individuals who carry the *PSEN1 E280A* autosomal-dominant, mutation-causing EOAD and do not meet criteria for MCI due to AD (Albert et al. 2011) or dementia due to AD (McKhann et al. 2011) and are, thus, in a preclinical phase of AD (Sperling et al. 2011b). The study also incorporates administration of placebo to individuals who are not *PSEN1 E280A* autosomal-dominant mutation carriers. This efficacy and safety study will be conducted at a single primary site and approximately three satellite sites in Colombia.

In the Colombian study, *PSEN1 E280A* autosomal-dominant mutation carriers who meet study eligibility criteria will be randomized in a 1:1 ratio to one of two treatment groups: crenezumab or placebo. Crenezumab will be administered either SC (720 mg Q2W) or IV (60 mg/kg Q4W). Matching placebo will be administered by the same routes at the same frequencies. The switch to the higher IV dose

(approximately 4-fold higher exposure to crenezumab) will be optional. Participants may decide whether to change from the current SC dosing to the IV dose; however, once IV dosing in a given participant has occurred, it is not intended for a participant to switch back to the lower SC dose. In order to maintain genotype blind and to have a genetic kindred control, a cohort of *PSEN1 E280A* mutation non-carrier kindred family members will also be enrolled in the study and dosed only with placebo.

The study includes three arms with approximately 100 participants per arm; two arms of participants with a *PSEN1 E280A* mutation randomized in a 1:1 ratio to crenezumab or placebo and a third arm of non-carriers randomized to placebo. Participants will receive the randomized treatment until the final participant has reached their final treatment visit at 260 weeks (see [Figure 1](#)).

[figure not shown]

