remain blinded to study drug treatment assignment during the blinded treatment period in Study Period A as well as during the Study Period B (see Section 3.8 for details on blinding). Following the *data snapshot date* for the Study Period A *primary readout*, selected members of the Sponsor team may become unblinded for the purpose of analysis and interpretation of Study Period A data. *During Study Period B, after the results of Study Period A are available, study participants may choose to learn their mutation carrier status (see Sections 3.8 and 3.9 for additional information).*

Participants will have the option to receive the same dose (720 mg SC Q2W or 60 mg/kg IV Q4W) they were receiving at the end of the Study GN28352 *Period A* or switch to the higher dose of 60 mg/kg IV Q4W if they have not already switched. See Section 3.2.2 for rationale for crenezumab dosage.

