In the current study, beginning with protocol Version 6, use of a higher dose (60 mg/kg IV Q4W) than previously used in this study will be offered to participants in addition to the dose already available (720 mg SC Q2W) as it provides participants with an opportunity to receive a dose that may provide greater efficacy. Participation in the study with treatment at a higher dose is at the discretion of the participant after discussion of the different dosing options.

Figure 3 Pharmacokinetic Profile Based on Modeling and Simulation Data for 60 mg/kg Crenezumab Administered Intravenously Q4W Compared with 15 mg/kg Crenezumab Administered Intravenously Q4W

Conc = concentration; Q4W = every 4 weeks.

Note: The dotted red line is the half maximal effective concentration (EC_{50}).

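### The ARIA-E continue rule equates the same dose with 60 mg/kg, which cannot be true for participants on 720 mg SC

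*Protocol*

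**What the plan says.** Protocol Section 3.5.2.2 opens its ARIA-E rules in general terms: "The following rules for the management of MRI-related findings apply for ARIA-E". For asymptomatic ARIA-E with BGTS below 4, the first instruction is "Continue study drug at the same dose (i.e., 60 mg/kg crenezumab"). The Synopsis, under the same heading, has the same instruction with the drug name misspelled: "Continue study drug at the same dose (i.e., 60 mg/kg crenazumab"). Neither place mentions route or restricts the rule to participants who have moved to IV.

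The trial has two regimens. Section 3.1 states: "Crenezumab will be administered either SC (720 mg Q2W) or IV (60 mg/kg Q4W"). The move to IV is voluntary. Section 3.2.2 says: "Participation in the study with treatment at a higher dose is at the discretion of the participant after discussion of the different dosing options". Section 3.2.1 keeps both regimens open in Study Period B: "Participants will have the option to receive the same dose (720 mg SC Q2W or 60 mg/kg IV Q4W"). The SC flowcharts run to the end of Period A (Appendix 2) and through Period B (Appendix 5).

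Section 4.3.1.3 also covers ARIA-E. It says when study drug is held, but it does not repeat the instruction to continue at the same dose.

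**The concern.** The abbreviation i.e. introduces a definition, so the text says that the dose to be continued is 60 mg/kg. For a participant on IV this is consistent. For a participant on 720 mg SC, keeping the same dose and giving 60 mg/kg are two different instructions. The wording also departs from the protocol's own usage: Section 3.2.1 uses the same phrase and names both regimens.

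This is an operative instruction during an event that Section 5.1.3 lists as being of special interest, and the sponsor relies on these rules for participant safety. Two sites could read it differently for the same MRI finding. The point remains live in Period B, where carriers who had placebo in Period A receive crenezumab, may do so by the SC route, and have an MRI scheduled at Week 105.

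Section 4.3.1.3 adds a second discrepancy to the same set of rules, at a BGTS of exactly 4.

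**Working it through.** **The protocol's own exposure figure.** Section 3.2.2 says that 720 mg SC every 2 weeks gives exposure similar to 15 mg/kg IV every 4 weeks. Then 60 / 15 = 4, which matches the roughly 4-fold higher exposure stated in Section 3.1. By the protocol's own account the two regimens are not the same dose.

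**Can the two be equal at any eligible weight?**

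Inputs: SC 720 mg every 2 weeks and IV 60 mg/kg every 4 weeks (Section 3.1); eligible weight 45 to 120 kg (Section 4.1.3).

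- SC total per 4 weeks: 2 × 720 = 1440 mg.
- IV total per 4 weeks: 60 × 45 = 2700 mg at the lower weight limit, and 60 × 120 = 7200 mg at the upper.
- Nominal ratio, IV to SC: 2700 / 1440 = 1.875 (about 1.9), and 7200 / 1440 = 5.0.
- SC total per 4 weeks in mg/kg: 1440 / 45 = 32.0, and 1440 / 120 = 12.0, against 60 for IV.
- Weight at which one SC dose equals 60 mg/kg: 720 / 60 = 12 kg.
- Weight at which the 4-week SC total equals 60 mg/kg: 1440 / 60 = 24 kg.

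Both weights lie well below the 45 kg entry limit, so the two halves of the instruction cannot both hold for any eligible participant on SC. The ratios are nominal milligrams with no allowance for SC bioavailability. They show only that the regimens differ, and do not measure a difference in exposure.

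**The ARIA-E rules side by side, for asymptomatic findings.**

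| BGTS | Synopsis and Section 3.5.2.2 | Section 4.3.1.3 |
|---|---|---|
| Below 4 | Continue at the same dose, defined as 60 mg/kg | Not among the reasons to hold |
| Exactly 4 | Interrupt | Not among the reasons to hold (threshold is above 4) |
| Above 4 | Interrupt | Hold |

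The first row holds the contradiction for SC participants. The second row is the separate conflict at a score of 4, which applies to both routes.

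**The case against.** The strongest reply is that no site would be misled. The operative verb is to continue, and an SC participant cannot continue an IV dose never received. Moving to IV is the participant's own choice and brings a different route, interval and flowchart; nothing in the protocol makes an asymptomatic MRI finding a trigger for it. The parenthesis is not literally true for participants on blinded placebo either, so a blinded site already has to read past it. It may be a slip of i.e. for e.g. All of this makes continuation of the current regimen the likely reading.

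A reader might go further and infer that SC participants have no continue rule at all. The documents do not support that. A later bullet in Section 3.5.2.2, covering a finding that is stable or smaller on the 4-week repeat MRI, keeps study drug going and names no dose or route. Section 4.3.1.3 lists ARIA-E as a reason to hold drug only with symptoms or above its threshold, again without regard to route. The SC flowcharts dispense by default. The practical gap is therefore small, although none of these places says what the same dose means for an SC participant.

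A reader might also infer that the wording affects the efficacy results. That is not shown. SAP Section 5.3.2 handles a change from SC to IV by treatment policy, using all observed values, and the events are rare. Inconsistent handling could also come to light, because Section 5.1.3 requires every ARIA-E to reach the sponsor within 24 hours.

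The reply reduces the likely consequence but leaves the contradiction in place. A safety instruction should not depend on sites disregarding the definition it gives.

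**Conclusion.** The instruction is wrong as written for participants on 720 mg SC. It is an internal inconsistency in the Synopsis and in Section 3.5.2.2, and it holds if any participant is on SC.

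Its reach is limited. Section 1.2.2.1 reports 5 patients with new ARIA-E across all crenezumab studies as of 12 December 2019, so few participants would meet the rule. The documents give no count of participants on SC, so it cannot be said that many are exposed to the ambiguity. Nor can the wording fairly be read as directing SC participants to the higher regimen; the nominal 1.9- to 5.0-fold difference would matter only under that strained reading and does not add weight to the point. The concern is clear, uniform handling of a safety event.

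The arithmetic assumes that weights stay within the entry range; a weight change would have to reach 24 kg to alter the conclusion. The conflict at a BGTS of exactly 4 needs no such assumption.

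**What to change.** Reconcile the ARIA-E text in the Synopsis and Section 3.5.2.2 with Sections 3.1 and 3.2.1. The sponsor's clinical team should state, in identical words in both places, how the rule for asymptomatic ARIA-E with BGTS below 4 applies to participants on each regimen. In the same revision, bring Section 4.3.1.3 and those two places to a single BGTS threshold for holding study drug. Which dose and which threshold apply is for the sponsor to decide; neither is proposed here.

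The cost is wording in the Synopsis and Sections 3.5.2.2 and 4.3.1.3, plus a notice to sites. No new procedure is needed.
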